### **16.4.2 Primary Immunogenicity Endpoint**

The primary immunogenicity analysis will be a comparison of GMTs for SARS-CoV-2 neutralizing antibodies at 14 days after the second dose (i.e. Day 36).

Therefore, GMTs and GMT ratios will be estimated by applying an analysis of variance (ANOVA) including the factor treatment group and study site. This will be done using log10 transformed data and taking the anti-log of the resulting point estimates for the least squares means, least squares means differences and the corresponding 95% CIs. Tukey's HSD test will be applied for pair wise comparisons.

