8 IMMUNOGENICITY ANALYSES

Immunogenicity samples (10ml) will be drawn for SARS-CoV-2-specific neutralizing antibody titre evaluation using wild-type virus microneutralization assay (WT-MNA) and binding IgG antibody titre evaluation by ELISA. In addition, a blood sample [approx. 50mL] will be collected to isolate PBMCs from all participants except sentinel participants for future investigation of cellular immune responses to VLA2001.

Serum samples to measure SARS-CoV-2 neutralizing antibody levels will be collected from participants on Day 1 (prior first vaccination), Day 8, Day 22 (prior second vaccination), Day 36, Day 106 and Day 208. An authorized laboratory will measure virus specific neutralizing antibodies to SARS-CoV-2 using wild-type virus microneutralizing assay (WT-MNA). In brief, infectious virus is incubated with sera. Virus susceptible cell monolayers are exposed to the test sera/virus mixture. Patches of infected cells (microplaques) are detected via an antibody pair specific for the SARS-CoV-2 RBD Spike protein and visualised using colored substrate. Neutralizing titer of test sera is expressed as ND₅₀; serum dilution at where 50% of virus is neutralized. The Part A Day 36 analysis was performed with values below the limit of quantification of the WT-MNA (ND₅₀=58; i.e titre <58) before the WT-MNA was fully validated and LLOQ values were replaced with a value of 29 (i.e LLOQ/2=29). All subsequent analyses are performed with values below the limit of quantification of the fully validated WT-MNA (ND₅₀=62; i.e titre <62) and values lower than LLOQs will be replaced by 31 (LLOQ/2= 31). For results given as e.g. ND₅₀>SDUL reported value will be replaced with the highest sample dilution tested (SDUL) in all analyses..

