8.1 ANALYSIS OF PRIMARY IMMUNOGENICITY ENDPOINT

The primary immunogenicity analysis will be a comparison of geometric mean titres (GMTs) for SARS-CoV-2 neutralizing antibodies at 14 days after the second dose (i.e. Day 36).

GMTs along with corresponding 95% CI will be estimated by applying analysis of variance (ANOVA) for \log_{10} transformed neutralizing antibody titre including the factors dose group and study site. Estimates (least squares means, least squares means differences and the corresponding 95% CIs) obtained from ANOVA will be back transformed (antilog_{10}) to get the estimates of GMT, and corresponding 95% CI. If ANOVA suggests dose group differences to be statistically significant then Tukey’s HSD test will be applied for pair wise comparisons of dose groups. The table will also include the following descriptive summary statistics: number of non-missing observations (n), median, minimum, maximum.

If \log_{10} transformed data is not normally distributed then GMTs (CI) will be calculated by taking the antilogarithm of the mean (CI) of the \log_{10} transformed titre. Also p-value from Kruskal Wallis test will be calculated to check if the results are significantly different among dose groups at 5% level of significance. If the test suggests significant p-value then pairwise group comparison will be performed using Dwass, Steel, Critchlow-Fligner (DSCF) multiple comparisons post-hoc procedure to determine which pair of dose groups differ significantly.

In addition, as an exploratory analysis, data for SARS-CoV-2 neutralizing antibodies for an external convalescent group of participants will be presented. All dose groups will also be compared with this group.

A graph overlaying scatter plot over box plots for SARS-CoV-2 neutralizing antibodies titres will be presented by visits and dose cohorts. Similar scatter plot will be presented for convalescent participants also.

In addition, reverse cumulative distribution functions will be plotted for SARS-CoV-2 neutralizing antibodies titres (ND50) by dose groups for scheduled visits Day 1, 8, 22, 36, 106, 208.

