8.2 ANALYSIS OF SECONDARY IMMUNOGENICITY ENDPOINTS

8.2.1 Immune Response as Measured by Neutralizing Antibody Titres Against SARS-CoV-2

The same methodology as described for primary endpoints will be used for analysis of neutralizing antibody titres against SARS-CoV-2 for all timepoints. Descriptive summary statistics including number of non-missing observations (n), median, minimum, maximum GMTs along with 95% CI for neutralizing antibody titres against SARS-CoV-2 will be presented over time for all sample visits.

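### An unspecified normality check in SAP 8.1 can replace the protocol's site-adjusted GMTs and GMT ratios with unadjusted ones, mainly because values below LLOQ are set to LLOQ/2

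*SAP*

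**What the plan says.** Protocol 16.4.2 states without condition that "GMTs and GMT ratios will be estimated by applying an analysis of variance (ANOVA) including the factor treatment group and study site", on the log10 scale with back-transformed least squares means, differences and 95% CIs, and Tukey's HSD for pairs.

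SAP 8.1 starts from the same model, "including the factors dose group and study site", and then adds a branch. If the log10 "transformed data is not normally distributed then GMTs (CI) will be calculated by taking the antilogarithm of the mean" of the log10 titre, a Kruskal-Wallis test asks whether results are "significantly different among dose groups at 5% level of significance", and pairs are compared by the "Dwass, Steel, Critchlow-Fligner (DSCF) multiple comparisons post-hoc procedure". The branch mentions neither site nor a between-group ratio.

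SAP 8.2.1 extends the rule: "The same methodology as described for primary endpoints will be used for analysis of neutralizing antibody titres against SARS-CoV-2 for all timepoints". SAP 8.2.3, 8.2.4 and 8.2.6, and 8.3.1, 8.3.3, 8.3.4 and 8.3.6, refer back to it for fold increases, ELISA titres and the booster phase.

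Before any of this, titres below the assay limit become a single constant. For the Part A Day 36 analysis, "LLOQ values were replaced with a value of 29" (limit 58). In all later analyses, "values lower than LLOQs will be replaced by 31" (limit 62).

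Protocol 16.4 requires a change to the planned analyses to be described and justified in the SAP. SAP 13.1, the list of changes, contains only the removal of stratification by serostatus.

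**The concern.** The estimator and the test for the primary endpoint depend on a feature of the data, through a check that two analysts could carry out differently and reach different branches. The two branches do not report the same thing. One gives site-adjusted GMTs and dose ratios with intervals. The other gives raw GMTs and rank-based p-values.

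The trigger can also be built in. Setting every value below LLOQ to one number puts a spike in the lower tail, and normality tests are sensitive to spikes. Because the rule runs separately at each visit and for each assay, one table could show adjusted GMTs at some visits and raw GMTs at others, with nothing in the estimand to explain the difference.

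**Working it through.** **1. The plan's own figure.** SAP 2.5 expects about 45 evaluable participants per dose group: 50 × (1 − 0.10) = 45.0. This reproduces. The documents give no titre SD, expected GMTs, share of values below LLOQ, number of sites or site variance, so the rest uses stated assumptions.

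**2. What each branch delivers.**

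| | Protocol 16.4.2 and main branch of SAP 8.1 | Fallback in SAP 8.1 |
|---|---|---|
| GMT | Least squares, adjusted for site | Antilog of plain mean |
| Between-dose ratio and CI | Yes (back-transformed difference) | None planned |
| Pairwise test | Tukey's HSD | DSCF |

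**3. Inputs for the switch rate.** Assumed: 3 × 45 participants, normal log10 titres within each dose, Shapiro-Wilk at 5%, and values below 62 set to 31 (limit and substitute from SAP 8). The expected share below LLOQ in one arm is Φ((log10 62 − log10 GMT)/SD). For GMT 150 and SD 0.4 this is Φ((1.792 − 2.176)/0.4) = Φ(−0.96), about 17%. For GMTs 250 and 500 it is about 6.5% and 1.2%, so the three-arm average is (16.9 + 6.5 + 1.2)/3 = 8.2%. The same formula gives averages of about 12% and 7% for the second and third rows below.

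**4. Simulated switch rates** (2,000 to 4,000 trials per run; ranges are across repeated runs).

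| GMTs low/medium/high | SD | Below LLOQ | Pooled data | Residuals | Pooled, LLOQ substitution removed |
|---|---|---|---|---|---|
| 150/250/500 | 0.4 | 8% | 61–64% | 14% | 4% |
| 150/250/500 | 0.5 | 12% | 94% | 21% | 5% |
| 150/300/900 | 0.4 | 7% | 42–44% | 13–14% | 5.5% |

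With the same dose gaps but no substitution, the pooled rate returns to about the nominal 5%. The substitution, not the dose effect, drives these rows. In the first row, checking each group separately and counting any failure gives 66%, so a by-group reading does not avoid the problem.

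**5. Dose separation alone** (normal errors, nothing below LLOQ, pooled check).
- High dose alone separated 3-fold: 10%, 5% and 4% at SD 0.3, 0.4 and 0.5.
- High dose alone separated 5-fold: 48%, 14% and 7%.
- Evenly spaced, 3-fold from low to high: 4% at each SD.
- Evenly spaced, 10-fold: 25%, 8% and 5%.
- GMTs 300/600/2400 at SD 0.3: about 38%, against 5–6% on residuals.

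Residual checks stay at 4–6% throughout the grid.

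**6. Does checking residuals cure it?** Not the LLOQ part. With equal GMTs of 150, SD 0.4 and about 17% below LLOQ, residuals are rejected in about 95% of trials.

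**7. Cost of dropping site.** If site explains a fraction R² of the variance, the standard error of a dose contrast grows by 1/√(1 − R²). R² = 0.10 gives 1.05 and R² = 0.20 gives 1.12. In a simulation with four sites and within-group SD 0.4, the 95% range of the unadjusted high/low GMT ratio divided by the adjusted one was 0.90–1.12, 0.83–1.20 and 0.77–1.31 for between-site SDs of 0.1, 0.2 and 0.3 log10.

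**The case against.** The fallback is written down in advance, with a multiplicity-adjusted pairwise procedure. SAP 2.2 says there are no formal hypotheses, so no controlled type I error is at stake. Protocol 10.5 describes 1:1:1 randomisation and states no stratification by site, so omitting site costs mainly precision. A reader can divide two reported GMTs to obtain a ratio. All of this stands and limits the consequence. It does not supply the missing interval for the ratio, define the trigger, or explain a departure that SAP 13.1 does not list.

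A reader might infer that the SAP tests pooled data and so abandons the ANOVA whenever the doses truly differ. The documents do not support that. The SAP does not say pooled, by group or residual, and even on pooled data a 2- to 3-fold difference leaves the switch rate near nominal in most settings. Protocol 8.5 calls the high-dose response superior but gives no GMTs, so the size of the separation is unknown.

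It is also tempting to say that Day 8 will switch, or that the Day 36 dose selection rests on the fallback. The documents give no share of values below LLOQ at any visit and do not show which branch was used at Day 36.

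**Conclusion.** The point holds as a pre-specification gap: an undefined check can displace the protocol's primary estimator, and the change is neither justified nor listed. LLOQ/2 substitution is the main trigger. With 7 to 12% of values below LLOQ, the switch occurs in roughly 44 to 94% of trials on pooled data. Dose separation is a secondary trigger that needs both a pooled check and a separation that is large relative to the SD. These rates depend on the assumed GMTs, SDs and Shapiro-Wilk test; the text of the two documents establishes the gap without them.

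The harm is to the definition of the primary estimate and its comparability across visits and assays. The fallback buys little in return, because its interval is still an interval for mean log10 titre. The point does not show that the Day 36 result or the dose choice is wrong.

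**What to change.** In SAP 8.1, make the ANOVA on log10 titre with dose group and site the primary analysis at every visit whatever any normality check shows, and always report GMT ratios with 95% CIs. Let the sections that refer back to 8.1 inherit this. Keep Kruskal-Wallis and DSCF as sensitivity analyses only. Where many values fall below LLOQ, add a left-censored (Tobit-type) model, also as sensitivity. Moving the check to residuals should not be offered as the remedy, since it leaves the LLOQ trigger in place.

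The Part A Day 36 analysis has been run, so new wording cannot alter it. State which branch was used there, and report the site-adjusted Day 36 GMT ratios in later reports. Table 14.3.1.1, planned for all three interim analyses, is a natural place. If the sponsor keeps any conditional rule, list and justify it in SAP 13.1.

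The cost is SAP wording and a little extra analysis. No new data are needed.

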8.2 ANALYSIS OF SECONDARY IMMUNOGENICITY ENDPOINTS

8.2.1 Immune Response as Measured by Neutralizing Antibody Titres Against SARS-CoV-2

The same methodology as described for primary endpoints will be used for analysis of neutralizing antibody titres against SARS-CoV-2 for all timepoints. Descriptive summary statistics including number of non-missing observations (n), median, minimum, maximum GMTs along with 95% CI for neutralizing antibody titres against SARS-CoV-2 will be presented over time for all sample visits.

8.2.2 Proportion of Participants With Seroconversion in Terms of Neutralizing Antibodies

Seroconversion will be defined as ≥ 4 -fold increase in SARS-CoV-2-specific neutralizing antibody titre levels between Day 1 and post-vaccination sample collection timepoints. The fold increase is defined as a participant's post-Baseline titre at a visit divided by the baseline (Day 1) titre. The number and proportion of participants with seroconversion in terms of neutralizing antibodies on Day 8, Day 22, Day 36, Day 106 and Day 208, in participants negative for SARS-CoV-2 infection at Screening will be presented along with exact 95% Clopper-Pearson confidence interval (CI) for each dose group and overall. Differences between the dose groups will be assessed for significance using Fisher-Freeman-Halton exact test and p-values will be presented for this test. If overall group difference is statistically significant, i.e. p-value for Fisher-Freeman-Halton exact test is ≤ 0.05 , then multiplicity adjusted p-values (using Hochberg method) for pairwise group difference will be calculated for Fisher's exact test.

In addition, the number and proportion of participants with ≥ 2 -fold increase, ≥ 10 -fold increase and ≥ 20 -fold increase will also be presented for each post baseline visit.

8.2.3 Fold Increase of SARS-CoV-2 Neutralizing Antibody Titres

Geometric mean fold increase (GMFI) of SARS-CoV-2 neutralizing antibody titres on Day 8, Day 22, Day 36, Day 106 and Day 208 compared with baseline will be estimated using the same methodology as described for the primary immunogenicity endpoint. In the ANOVA model the dependent variable \log_{10} titre will be replaced with \log_{10} fold increase.

8.2.4 Immune Responses as Measured by IgG anti SARS-CoV-2 IgG S-ELISA

The same methodology as described for primary endpoint will be used for the summary and analysis of IgG antibody titres determined by ELISA. The analysis will be presented for each of the scheduled sampling timepoint i.e. Day 1, 8, 22, 36, 106 and 208.

A graph overlaying scatter plot over box plots for IgG antibody titres will be presented by visits and dose cohorts.

8.2.5 Proportion of Participants With Seroconversion In Terms of IgG Antibodies Against SARS-CoV-2 As Determined By ELISA

The same methodology as described in section 8.2.2 will be used for the summary and analysis of proportion of participants with seroconversion in terms of IgG antibodies. Seroconversion will be defined as ≥ 4 -fold increase in SARS-CoV-2-specific IgG antibody levels between Day 1 and post-vaccination sample collection timepoints.

8.2.6 Fold Increase of SARS-CoV-2 IgG measured by anti-SARS-CoV-2 S-ELISA

Geometric mean fold increase (GMFI) of SARS-CoV-2 IgG antibody titres on Day 8, Day 22, Day 36, Day 106 and Day 208 compared with baseline will be estimated using the same methodology as described for the primary immunogenicity endpoint. In the ANOVA model the dependent variable \log_{10} titre will be replaced with \log_{10} fold increase.

8.3 ANALYSIS OF SECONDARY IMMUNOGENICITY ENDPOINTS FOR THE BOOSTER PHASE

Analysis for booster phase will be presented for booster group ITT population.

8.3.1 Geometric mean fold rise (GMFR) for SARS-CoV-2 Neutralizing Antibody Titres

Geometric mean fold rise (GMFR) of SARS-CoV-2 neutralizing antibody titres at Visit 8 and Visit 9 compared with pre-booster time point (Visit 7) and corresponding CI will be calculated using the same methodology as described for the primary immunogenicity endpoint.

The fold increase will be calculated as a participant's titre at a visit divided by the pre-booster time point (Visit 7) titre.

8.3.2 Proportion of Participants With 4-fold increase in Terms of Neutralizing Antibody Titres

The number and proportion of participants with 4-fold increase from pre-booster dose (Visit 7) to Visit 8 and Visit 9 in terms of neutralizing antibodies will be presented. Exact 95% Clopper-Pearson confidence interval (CI) will also be presented for proportions.

8.3.3 Geometric mean titres (GMT) for SARS-CoV-2 Neutralizing Antibody Titres

GMTs along with corresponding 95% CI for neutralizing antibodies will be calculated using the same methodology as described for the primary immunogenicity endpoint. The results will be presented for Visit 7, Visit 8 and Visit 9.

8.3.4 Geometric mean fold rise (GMFR) for S-protein binding antibodies (ELISA)

Geometric mean fold rise (GMFR) of S-protein binding antibodies (IgG antibody titres) measured by ELISA at Visit 8 and Visit 9 compared with pre-booster time point (Visit 7) and corresponding CI will be calculated using the same methodology as described for the primary immunogenicity endpoint.

8.3.5 Proportion of Participants With 4-fold increase in Terms of S-protein binding antibodies (ELISA)

The number and proportion of participants with 4-fold increase from pre-booster dose (Visit 7) to Visit 8 and Visit 9 in terms of S-protein binding antibodies (IgG antibody titres) will be presented. Exact 95% Clopper-Pearson confidence interval (CI) will also be presented for proportions.

8.3.6 Geometric mean titres (GMT) for S-protein binding antibodies (ELISA)

GMTs along with corresponding 95% CI for S-protein binding antibodies (IgG antibodies against SARS-CoV-2, as determined by ELISA) will be calculated using the same methodology as described for the primary immunogenicity endpoint. The results will be presented for Visit 7, Visit 8 and Visit 9.

9 EXPLORATORY ANALYSES

9.1 IFN Gamma T-CELL ELISpot (T-SPOT)

The cell-mediated (cellular) immune response (T-cell response) will be assessed on Day 1, Day 36 and Day 208 by IFN gamma T-cell ELISpot assays to SARS-CoV-2 antigens.

For T-cell ELISpot assay, the isolated PBMCs are incubated with SARS-CoV-2 specific peptides to allow stimulation of any SARS-CoV-2 antigen specific T-cells present. Secreted cytokine, e.g. IFN-gamma, is captured by specific antibodies on the membrane which forms the base of the plate well, PBMCs and other unwanted materials are removed by washing. A secondary conjugated antibody directed to a different epitope of the cytokine molecule, is added and binds to the cytokine captured on the membrane. A soluble substrate is added and cleaved by the conjugate to form a spot of insoluble precipitate at the site of reaction. Each spot represents the footprint of the individual cytokine-secreting T-cell and evaluating the number of spots obtained provides a measurement of the abundance of antigen specific effector T-cells in peripheral blood. Results are reported as number of spot forming units (SFU) per 250 000 PBMCs. SFU for each stimulation panel are normalized to the negative control (SFU of Nil control are subtracted). The sample is considered reactive against individual stimulation panel if the normalized SFU ≥ 6 .

Results of the cellular immune response will be summarized descriptively by dose group and overall and will be presented for both the PPAS and modified PPAS for each visit and stratified for T-spot baseline reactivity (“Reactive on Day 1” and “Non-Reactive on Day 1”). A sample is considered ‘Reactive’ at baseline (Day 1) if the normalized SFU ≥ 6 in at least one SARS-CoV-2 specific stimulation panel (i.e. Panel 1, 2, 3, 4, 14) on Day 1. In addition, the p-value from Kruskal Wallis test will be calculated to check if the results are significantly different among dose groups for each stimulation panel. If the test suggests a significant p-value, then a pairwise group comparison will be performed using Dwass, Steel, Critchlow-Fligner (DSCF) multiple comparisons post-hoc procedure to determine which pair of dose groups differ significantly. In addition, a Signed Rank Test will be performed within each dose group to test for significant difference between tested days (i.e. Day 1 vs Day 36, Day 1 vs Day 208, Day 36 vs Day 208) for each stimulation panel.

Following parameters will be summarized:

- Panel 1 Spike Protein N terminus
- Panel 2 Spike Protein C terminus
- Panel 3 Nucleocapsid Protein
- Panel 4 Membrane Protein
- Panel 13 A cross reactive pool of coronavirus epitopes
- Panel 14 Spike Protein, full sequence

A graph overlaying scatter plot over box plots presenting the above mentioned parameters of ELISpot (Spot forming units/ 2.5×10^5 PBMC) will be presented by dose groups and assessment days per stimulation panel.

Booster Phase:

The cell-mediated (cellular) immune response (T-cell response) will be assessed on Visit 7 and Visit 8 of the booster phase by IFN gamma T-cell ELISpot assays to SARS-CoV-2 antigens.

Results of the cellular immune response will be summarized descriptively and will be presented for the booster group ITT population for each visit in the booster phase.

9.2 INTRACELLULAR CYTOKINE STAINING (ICS)

The Intracellular cytokine staining assay has been designed to measure cytokine production following stimulation of isolated cryopreserved PBMCs from vaccinated individuals with peptide pools. In brief, cryopreserved cells are thawed, then stimulated overnight with a pool of overlapping peptides derived from the SARS-CoV-2 spike protein (Panel 14), nucleocapsid protein (Panel 3), or control protein phytohemagglutinin (PHA). Following stimulation, the cells are stained for surface markers, fixed and permeabilised and then stained for intracellular cytokines. Following cytokines are assessed: Th1: IFN γ , IL-2, TNF α and Th2: IL-4, IL-5, IL-13. The percentage of positive cells among CD4+ and CD8+ T-cells was assessed for (1) each singular functional marker and stimulating peptide (single positives); (2) all permutations of 2 markers and stimulating peptide (double positives); (3) three cytokines specific for Th1 or Th2 response per stimulating peptide (triple positives).

Descriptive statistics will be presented for each singular cytokine (i.e. TNF+, IFNG+, IL-2+, IL13+, IL5+, IL4+) and stimulation panel (i.e. P3, P14, PHA). This will be presented by dose group and overall and for both the PPAS and modified PPAS. Following visits will be presented: Day 1, Day 36, Day 208.

In addition, graphs presenting percentage of positive cells among CD4+ and CD8+ T-cells for each participant will be presented by each visit and dose group for each singular cytokine ((i.e. TNF+, IFNG+, IL-2+, IL13+, IL5+, IL4+) and stimulation panel (i.e. P3, P14, PHA).

For the second interim analysis (Day 106 Analysis), ICS data will be analyzed and presented in TLFs only for the high dose group.

ICS results for singular cytokines will also be presented in participant data listings.

Booster Phase:

Descriptive statistics will be presented for each singular cytokine (i.e. TNF+, IFNG+, IL-2+, IL13+, IL5+, IL4+) and stimulation panel (i.e. P3, P14, PHA). This will be presented for the booster group ITT population. Following visits will be presented: Visit 7 and Visit 8.

ICS results for singular cytokines will be presented in participant data listings separately for the booster phase.

